3.2.2.2 The use of Magnetic Resonance Elastography to evaluate liver fibrosis

MR elastography uses a vibrating passive driver or “paddle” placed on the abdominal wall over the liver in order to generate *in vivo* shear waves. These shear waves can be tracked using an MRI modified phase contrast pulse sequence. Shear wave data is then used to generate color parameteric maps (elastograms) of liver stiffness that allow quantitative assessment (Figure 4). We have demonstrated excellent agreement when using intra-class correlation coefficients to assess reproducibility of MR elastography measurements across MRI scanners (Philips and GE Healthcare), field strengths (1.5T and 3T), and pulse sequences in 24 adult healthy volunteers. Pairwise ICCs ranged from 0.67-0.82 when agreement was assessed between individual sequences across manufacturers (GE vs. Philips); the greatest agreement while fixing the pulse sequence was at 1.5T using 2D GRE sequences (ICC=0.82, r=0.85) (16).

A study by Wallihan et al (11) showed that MRI-derived liver stiffness was universally elevated in a cohort of children and young adults that had undergone the Fontan procedure. They also found a statistically significant inverse correlation between liver stiffness and cardiac index ($p=0.02$) and ejection fraction ($p=0.002$). Patients with long Fontan duration (>20 years post-op) had greater liver stiffness compared with those having a shorter duration ($p=0.02$). The study provided evidence that elevated liver stiffness in Fontan patients is likely due to both fibrosis and congestion.

Figure 4: 13 year-old patient status post Fontan palliation due to Single Ventricle Congenital Heart Disease.

A, MR elastography color wave image shows mechanically-induced shear waves in the liver. **B**, Color parametric map (elastogram) shows the distribution of stiffness within the upper abdomen, including the liver. The liver is very stiff and heterogeneous.

3.2.2.3 Biomarkers and liver stiffness

As noted previously, increased liver stiffness can be secondary to hepatic congestion and/or hepatic fibrosis. Circulating biomarkers previously demonstrated to be associated with congestive heart failure or tissue fibrosis may help to determine the primary driver of liver stiffness in a particular patient and help to monitor the response to targeted therapy. For instance, we would anticipate that patients with increased liver stiffness due to hepatic congestion would have increased biomarkers of heart failure (e.g., BNP, NT-proBNP). Similarly, patients in whom fibrosis significantly contributes to increased liver stiffness may have elevation in biomarkers associated with liver fibrosis (e.g., ELF panel, miR-138, miR-143, or galectin-3). The relative contribution of congestion or fibrosis (as determined by biomarker profiles) to the observed level of liver stiffness may correlate with which therapeutic strategies are likely to be successful in a particular patient. Therefore, in this aim, we will determine which circulating biomarkers correlate with measures of liver stiffness and which correlate with a change in liver stiffness with udenafil treatment. We will use both a directed approach, with an analysis of candidate biomarkers validated for other disease processes, and a non-directed approach, which will identify novel biomarkers potentially associated with FALD.

4.0 CLINICAL TRIAL OBJECTIVES, AIMS, AND HYPOTHESES

4.1 Clinical Trial Objective

Determine scope of hepatic stiffness in Fontan patients by ultrasound and magnetic resonance imaging elastography and evaluate the efficacy of udenafil in reducing liver stiffness.

4.2 Primary Aim and Hypothesis

Primary Aim: Define the range of liver stiffness in those who have had the surgical creation of a total cavopulmonary connection.

Hypothesis: Following total cavopulmonary connection, children with single ventricle congenital heart disease will have elevated measures of liver stiffness.

4.3 Secondary Aims and Hypotheses

Secondary Aim 1: Determine the impact of udenafil treatment on liver stiffness in a large cross-section of adolescents who have undergone total cavopulmonary connection.

Hypothesis: Udenafil treatment will reduce liver stiffness as measured by non-invasive elastography by decreasing venous congestion.

Secondary Aim 2: Determine the relationship between clinical outcomes and liver stiffness.

Hypothesis: Liver stiffness will be associated with measures of ventricular diastolic function, exercise performance, and endothelial function.

Secondary Aim 3: Assess the association between biomarkers of both heart failure and liver fibrosis and liver stiffness.

Hypothesis: Biomarkers of heart failure and liver fibrosis will directly correlate with liver stiffness as measured by ultrasound and magnetic resonance elastography.

5.0 STUDY DESIGN

This is an open-label extension study that integrates with the FUEL Extension Trial. FUEL-enrolled patients will have been randomized and double-blinded to either placebo or udenafil, and all patients entering the FUEL Extension trial will be placed on udenafil therapy. Therefore, approximately 50% of patients eligible to be enrolled in our study will be udenafil-naïve (U-) and 50% will have already completed 6-months of therapy (U+). As a part of FUEL-OLE, each participant will receive one year of udenafil treatment (87.5 mg twice daily). Both the U- cohort and the U+ cohort will have liver stiffness measured by ultrasound and MR elastography (where available), as described above. Thus, the U- subjects will have elastography measurements pre-udenafil and after 1 year of treatment. This will determine the impact of udenafil therapy on liver stiffness. Additionally, the U+ cohort from FUEL will allow us to determine if potential benefits of udenafil therapy are sustained over time by comparing measurements after 6 (baseline entry into our study) and 18 months of therapy (after 1-year of our study). The study visits are as follows:

1. Baseline visit: during the baseline visit, subjects will undergo ultrasound SWE and, if available at their center, magnetic resonance elastography. These will be coordinated with FUEL extension testing to ensure that the primary study is not interrupted. The additional blood work for this protocol will be obtained at the same time as the blood work for the FUEL extension study.
2. Follow-up visit: during the follow-up visit, subjects will undergo ultrasound SWE and, if available at their center, magnetic resonance elastography. These will be coordinated with FUEL extension testing to ensure that the primary study is not interrupted. The additional blood work for this protocol will be obtained at the same time as the blood work for the FUEL extension study.

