3.0 BACKGROUND INFORMATION AND RATIONALE

3.1 Discussion of Hepatic fibrosis and FUEL Trial Extension Study

3.1.1 FALD

Fontan-associated liver disease (FALD) is defined as abnormalities in liver structure and function resulting from the abnormal circulation created by the total cavopulmonary connection (TCPC) and not related to any other process (1). FALD is increasingly recognized as one of the most common complications of the TCPC (2, 3) and one which is universally present in patients with TCPC physiology (8-11). After the Fontan operation, blood from the inferior and superior vena cava are routed directly to the pulmonary arteries bypassing the heart (Figure 1). In this circulation, blood is not “pumped” through the lungs but is “pushed” through by chronic elevation of the central venous pressure. It is postulated that the Fontan’s elevated, non-phasic systemic venous pressure results in obligate chronic hepatic venous hypertension and congestion that is likely an important driver of hepatic fibrosis. As part of the injury response, activated myofibroblasts deposit excess extracellular matrix in the perisinusoidal space, a process which, if it persists, can lead to increased hepatocellular injury, progressive fibrosis, organ dysfunction, and, ultimately, to cirrhosis and hepatic failure. The congestion and fibrosis result in a wide spectrum of liver disease, including synthetic dysfunction, ascites, portal hypertension, cirrhosis, and hepatocellular carcinoma, and may culminate in fulminant liver failure. The severity of liver fibrosis is known to increase with time after TCPC and occurs in the absence of any other identifiable etiology of chronic liver disease.

Figure 1: Description of Fontan Associated Liver Disease

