9.4.3 Secondary Outcomes

Secondary outcome 1

Baseline liver stiffness measured by ultrasound or MRI elastography will be compared between the two groups (U+ vs. U-) using appropriate statistics. Next we will assess change in liver stiffness from pre- to post-1 year udenafil treatment in the U-group as well as from 6 to 18 months of therapy in the U+ group.

Secondary outcome 2

Changes in liver stiffness, diastolic cardiac function (including E/E' and MPI), PAT measurement, and exercise measurements (including peak VO₂ and submaximal exercise measures) from baseline to 12 months will be quantified. Correlation between change in liver stiffness and changes in diastolic cardiac function and exercise measurements in the entire cohort and in the U- group and U+ group separately.

Secondary outcome 3

Bivariate analyses will examine 1) the correlation between each biomarker and liver stiffness measured by ultrasound and MRI elastography and 2) the correlation between change in each biomarker and change in liver stiffness from baseline to 12 months in both the U+ and U- cohorts.

The proteomic and transcriptomic data will be presented primarily as a descriptive report. Pairwise differences between groups may be sought using appropriate 2-group statistics, but we expect the limited sample size in this exploratory outcome to limit analysis to descriptive statistics.

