10.7 Study Limitations

While integrating with FUEL-OLE is a clear advantage and makes this FALD study feasible, the study will not have a placebo control arm. However, an active control (U+) should still allow assessment of how udenafil affects liver stiffness in a naïve patient. Each center may have access to only US SWE, MR elastography, or both. We expect most, if not all, centers to have access to US SWE, as it is now widely available, commonly employed in practice, and straightforward to use. Our (CCHMC) radiology core (including MRI physicist [name], and imaging post-processing laboratory) will be able to facilitate MR elastography capabilities at participating centers, ensuring the use of a standardized protocol across scanners. Experience in processing and analyzing/interpretation of this relatively new measurement technique should be mitigated by use of a radiology core. MR elastography is more difficult to add for currently non-capable centers, thus, MR elastography measurements will be limited to centers that have capabilities.

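### Secondary Aim 1 takes udenafil's effect from the U- before-after change, which includes a year of natural course, and does not identify the entry U+ versus U- comparison as its only randomised placebo contrast

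*Combined protocol and SAP*

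**What the plan says.** - **Allocation before entry.** Section 5.0: "FUEL-enrolled patients will have been randomized and double-blinded to either placebo or udenafil". About half of those eligible arrive untreated (U-) and half after 6 months of udenafil (U+).
- **Masking and timing.** Section 9.3 unblinds FUEL assignments only when FUEL-OLE is complete. Section 11.1 places entry imaging on the morning of the second extension day, ahead of that day's study drug.
- **Where the drug effect is to come from.** Section 5.0: "Thus, the U- subjects will have elastography measurements pre-udenafil and after 1 year of treatment", followed by "This will determine the impact of udenafil therapy on liver stiffness". U+ is given a different question: "the U+ cohort from FUEL will allow us to determine if potential benefits of udenafil therapy are sustained over time".
- **Analysis.** Section 9.4.3, secondary outcome 1: "Baseline liver stiffness measured by ultrasound or MRI elastography will be compared between the two groups (U+ vs. U-) using appropriate statistics". The change within U- and the change within U+ come next. No between-group test of change is listed.
- **Sizing.** Section 9.2 introduces this outcome as a comparison with patients on continuing udenafil, but the tests it names are paired tests within each group.
- **Control.** Section 10.7: "the study will not have a placebo control arm". It offers U+ as an active control.
- **Natural course.** Section 3.1.1: "The severity of liver fibrosis is known to increase with time after TCPC".

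**The concern.** Section 5.0 makes a causal claim for a single-group before-after change in a disease that the protocol itself describes as progressive. If stiffness rises over the year for reasons unrelated to the drug, a real benefit will look smaller or absent in U-. In U+, a sustained benefit could look as if it were wearing off.

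The one comparison in which natural course cancels by randomisation is the entry scan. It carries no label as a treatment effect, no named test, no interval and no power statement.

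Secondary Aim 1 is the study's efficacy question and the one on which the sample size is built. Section 3.1.3 would take a sustained reduction in stiffness as a reason to consider earlier treatment. What the headline estimate measures therefore matters.

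**Working it through.** **1. What each comparison estimates.** Let D(t) be the effect of t months of udenafil compared with none (negative is benefit), and G the natural 12-month change (positive is stiffening).

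| Comparison | Estimates |
|---|---|
| U+ minus U- at entry | D(6) |
| Change within U- | D(12) + G |
| Change within U+ | D(18) − D(6) + G |
| U- change minus U+ change | D(12) − D(18) + D(6) |

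G remains in both within-group changes. It cancels in the difference of changes, but that difference equals a drug effect only if the effect is complete by 6 months and then holds, because U+ stays on drug throughout. Only the entry comparison is free of both G and an assumption about the time course.

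**2. Direction and size of the distortion.** If G is positive, D(12) + G lies nearer zero than D(12), so a benefit is understated. The documents give no value for G in 12-month stiffness. For illustration only, assume G of 2% to 5%. A true −10% would then appear as −8% (−10 + 2) to −5% (−10 + 5) in U-. U+ would rise by 2% to 5% with no loss of effect.

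**3. The plan's own sample size.** Inputs from section 9.2: mean 2.08 m/s, SD 0.24, 10% reduction = 0.208 m/s, 85% power, alpha 0.05 (taken as two-sided).

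Paired normal approximation, with 0.24 as the SD of the change: n = [0.24 × (1.960 + 1.036) / 0.208]² = 11.95, so 12.

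This reproduces the stated 12 per group, as a within-group calculation. Compared between two groups, 12 per arm would have 53% (t) to 56% (normal) power. The entry contrast therefore has no sizing of its own.

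**4. Power of the entry contrast.** Same inputs, two independent groups: n per group = 2 × 11.95 = 23.9, so 24 by the normal formula and 25 by the two-sample t-test. That is 48 to 50 in total, at the lower end of the 50 to 150 planned in section 6.1.

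Two-sample t-test, two-sided 0.05:

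| Per group | Power for 10%, SD 0.24 | Detectable at 85% power, SD 0.24 | Power for 10%, SD 0.36 (assumption) |
|---|---|---|---|
| 25 | 85% | 10.0% | 52% |
| 50 | 99% | 7.0% | 82% |
| 75 | >99.9% | 5.7% | 94% |

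The approximate 95% CI half-width at SD 0.24 is 1.96 × 0.24 × √(2/n): 0.133 m/s (6.4% of 2.08) with 25 per group and 0.094 m/s (4.5%) with 50.

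The wider SD is shown because 0.24 comes from patients 6 months after the operation. Adolescents aged 12 to 19, scanned at several centres, may vary more.

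**The case against.** The strongest reply is that the comparison is already in the plan and little more than its label is at issue. Much of this stands.

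- **A reader might infer that the randomised contrast is missing, or kept only as a balance check.** The documents do not support that. Section 9.4.3 lists it first under the outcome for the udenafil aim. The synopsis places efficacy assessment at both the start and the end of the extension, and names absolute stiffness as well as change. In section 5.0, baseline is the name of a visit. The gap is that nothing identifies the comparison as the drug effect.
- **A reader might infer that the U- change has no comparator at all.** Section 9.2 speaks of comparison with continuing udenafil, and section 10.7 names U+ as a control. But no analysis in section 9.4.3 carries this out.
- **A reader might infer that section 10.7 is false.** It is literally true of this study's 12 months, and it is an open disclosure. It needs an addition, not a reversal.
- **A reader might call the entry contrast unbiased.** It sees only FUEL participants who entered the extension, consented (50% to 75% expected) and attended a capable centre. No pre-randomisation scan is described. Section 11.1 says the last FUEL day and the first extension day are often, not always, the same visit, so some U+ patients may have been off drug when scanned, which would dilute the difference.
- **The size of the bias is unknown.** Section 3.1.1 concerns fibrosis over an unstated period. The only result on stiffness and duration, in section 3.2.2.2, contrasts more than 20 years with less, which is outside this age range. The hypothesised mechanism is relief of congestion, so an effect complete by 6 months is plausible, though not shown.
- **Paired change has its own advantage.** It largely removes differences between patients, sites and devices, which the entry contrast carries in full.

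None of this rescues the causal sentence in section 5.0. The within-group changes face the same selection at entry and add confounding with time. The SAP promised in section 9.1 could settle the analysis, but it would not alter what section 5.0 now claims.

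**Conclusion.** The point holds as one of identification and emphasis. The U- before-after change cannot by itself determine udenafil's effect: it is the net of treatment and natural course. If the liver stiffens over the year, the error runs towards hiding a benefit, by an amount the documents do not give. The entry U+ versus U- difference is the study's only randomised, masked udenafil-versus-placebo estimate, and the plan should say so.

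The entry contrast is workable within planned enrolment if the SD is near 0.24 and the groups are about equal, and marginal at the minimum of 50 if the SD is nearer 0.36. It is a 6-month estimate in selected extension entrants, and should carry that description. The primary aim is descriptive and unaffected. The change is still worth making, because this is the study's efficacy question and the remedy is cheap.

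**What to change.** 1. **Section 9.4.3, secondary outcome 1.** Report the entry U+ minus U- difference in stiffness, with a 95% CI and by FUEL randomised assignment, as the placebo-controlled 6-month estimate for Secondary Aim 1. Name the test and add a power statement. Say that it is not a balance check.
2. **State its limits beside it.** It covers 6 months only, in extension entrants who consented at capable centres, with no pre-randomisation scan and possible time off drug before entry. Report the numbers entering by FUEL arm.
3. **Keep the within-group 12-month changes as supportive.** If the comparison with ongoing udenafil in section 9.2 is intended, list it in section 9.4.3 with the assumption it needs: effect complete by 6 months and maintained.
4. **Section 5.0.** Replace the causal sentence with one saying that the U- change is the net of treatment and natural course.
5. **Section 10.7.** Add that the lack of placebo control applies after entry.

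The cost is protocol wording and a paragraph in the SAP, which section 9.1 says will be finalised before database lock. No scan, visit or patient is added, since both the entry imaging and the comparison are already planned.

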11.0 REGULATORY/ADMINISTRATIVE PROCEDURES AND DOCUMENTATION

11.1 Data Collection

Data for each SWE and magnetic resonance elastography will be generated from each site and recorded on a case report form. This form will serve as the source document for each test and will be used to enter data into an electronic data capture (EDC) system (eCOS). US SWE data will be recorded from each site. MREL data will need to be sent anonymized to CCHMC for central processing/analysis.

The biomarker core lab will generate results for each blood specimen and will transmit that data electronically into the EDC system (eCOS). Subject identification will follow the same system as for the FUEL Extension trial. Each imaging study will be associated with the FUEL Extension identification number and each blood sample will be labeled with that same number.

FUEL-OLE enrollment takes place over a 2 day period. For clarity, often the initial FUEL-OLE day (called hereafter OLE-D1) and the final day of FUEL are the same visit. This visit consists of informed consent and assent, blood sample collection, EndoPAT testing, an echocardiogram, and exercise testing. Based on experience with the Udenafil study, this day takes 5-6 hours in total. Subjects will then return the next day (OLE-D2) for drug administration and 6-minute walk. Subjects will return at 12 months of FUEL-OLE for a final day repeating the above tests. FALD will ideally be integrated into this schedule with keen attention to preserving the integrity of the FUEL-OLE parent trial and preventing study fatigue as detailed below for each step. This plan was vetted and approved by the FUEL study subcommittee.

Subject recruitment: FALD will only be recruited by either the site PI or a study coordinator after a commitment is given to participate in FUEL-OLE. Recruiting should be done at the same time point as OLE to prevent unnecessarily repetitive patient contact.

Consent/Accent: Consent and assent for FALD will be obtained immediately following but only after consent/assent for FUEL-OLE has been obtained.

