Serum testing: Serum for the ancillary study will be obtained during the same venipuncture as used in FUEL-OLE. The serum sample will be processed, stored and shipped in parallel with the plasma sample that is being collected for the FUEL-OLE Trial. The processed serum (and the processed plasma for the FUEL-OLE protocol) will be shipped to the FALD core lab (University of Michigan) for testing. The ancillary study will require an additional 3 ml sample of blood (for a total of 6 ml).

Imaging: We have identified the morning of OLE-D2 as the optimal time for hepatic imaging.

[figure not shown]
Page 30 of 35

- US SWE: A complete US SWE exam lasts 5-10 minutes only. It is a portable test, and thus may be performed in either a radiology suite or any other clinical cardiology location used by the study. Additional limited anatomic imaging will also be obtained that takes approximately 1 minute.
- MRE: A complete MRE exam lasts approximately 15-20 minutes. Additional limited anatomic imaging will also be obtained that takes approximately 1 minute. Including patient travel to and from the MR scanner we anticipate an additional 20-40 minutes, making the total duration of MR testing 35-60 minutes.

All liver imaging should be able to be completed in 60-90 minutes.

- For initial FALD imaging, by starting OLE-D2 immediately with hepatic imaging at 7:30 or 8:00 AM, we would anticipate FUEL-OLE can begin its formal day's schedule with study drug administration by 9-9:30 AM. In total, we would expect OLE-D2 including hepatic imaging to still conclude by midday as anticipated by the FUEL-OLE protocol.
- For the OLE and FALD 12-month follow-up visit, we would again anticipate beginning the day for with hepatic imaging. To make this feasible, we can pay for hotel costs for those individuals enrolled in FALD at the 12-month visit so that the testing day may start early. Alternatively, imaging may be obtained at the end of the day following FUEL-OLE testing, although this is less ideal because exercise testing may influence FALD measures. Integration of same day testing should be feasible based on projected length of the testing day.

Imaging identifiers for these research studies will include only the site and subject study-specific ID. Following image obtainment at both time points, images from both US SWE and MRE will be sent to the imaging core. Images transferred will contain the site and subject identifiers and no protected health information.

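### U+ entry scans are all counted as on-treatment 6-month values, yet they precede the first extension dose and may follow an interruption when the FUEL and extension visits are separate

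*Combined protocol and SAP*

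**What the plan says.** Section 5.0 uses the U+ cohort to learn whether any benefit of udenafil lasts, "by comparing measurements after 6 (baseline entry into our study) and 18 months of therapy". Section 9.4.3 repeats the label for secondary outcome 1: change is assessed in the U- group over the treatment year, "as well as from 6 to 18 months of therapy in the U+ group". The same section adds that entry stiffness "will be compared between the two groups (U+ vs. U-) using appropriate statistics". Neither section sets a condition on drug status at the scan.

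Section 11.1 gives the schedule:

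- On the link between the two trials: "often the initial FUEL-OLE day (called hereafter OLE-D1) and the final day of FUEL are the same visit".
- On the first extension dose: "Subjects will then return the next day (OLE-D2) for drug administration and 6-minute walk".
- On the scan: "We have identified the morning of OLE-D2 as the optimal time for hepatic imaging".
- On the order within that morning, imaging starts at 7:30 or 8:00 AM, after which "we would anticipate FUEL-OLE can begin its formal day's schedule with study drug administration by 9-9:30 AM".

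Section 5.1 places the final scan at the 12-month completion visit. Section 11.1 prefers that scan at the start of the day but also permits it at the end, after the other tests.

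The hypothesis for Secondary Aim 1 in section 4.3 is: "Udenafil treatment will reduce liver stiffness as measured by non-invasive elastography by decreasing venous congestion".

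**The concern.** A scan labelled as 6 months of therapy should reflect the liver while the patient is on treatment. The planned scan comes before any extension dose. How long after the last FUEL dose it comes depends on whether the two visits coincided, and the plan accepts that sometimes they do not.

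The proposed mechanism is relief of congestion. If that effect fades without drug, a U+ subject scanned after an interruption reads stiffer at entry than on treatment. Resuming drug then produces a fall by month 12. Three readings would suffer:

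- The U+ change would look like sustained or growing benefit, and could hide a real loss of benefit.
- The entry difference between U+ and U-, the contrast that derives from FUEL's randomisation, would shrink.
- Any comparison of change between U- and U+ would shrink too, because U+ would show a fall of its own. Section 10.7 relies on U+ as the active control because there is no placebo arm.

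**Working it through.** **1. Order of events at entry (sections 5.0, 9.4.3, 11.1).**

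| Situation | Last FUEL day | OLE-D1 | Entry scan | First extension dose |
|---|---|---|---|---|
| Same visit | Day 0 | Day 0 | Day 1, from 7:30 or 8:00 AM | Day 1, by 9-9:30 AM |
| Separate visits | Day 0 | Day k, k not limited | Day k+1, same hours | Day k+1, same hours |

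In both rows the scan precedes the first extension dose. In the first row the scan is the morning after the last FUEL day. In the second row the interval is unbounded in these documents. They do not say when FUEL dosing stops or whether it continues to OLE-D1 or OLE-D2. They name no data item for last-dose date or time.

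**2. The plan's own figure (section 9.2).** Inputs: mean 2.08 m/s, SD 0.24, 10% reduction, 85% power, alpha 0.05.

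- Effect: 0.10 × 2.08 = 0.208 m/s.
- Two-sided one-sample normal approximation: n = [0.24 × (1.960 + 1.036) / 0.208]² = 11.95, so 12 per group.

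The stated 12 per group is reproduced, with 0.24 acting as the SD of the change. The present point does not depend on this sample size; the check only fixes the effect and SD used below.

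**3. Size of the possible bias (assumptions, not plan figures).** Let f be the fraction of U+ scanned at entry after an interruption, and g the share of a 10% effect lost by then. The U+ entry mean is too high by

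bias = f × g × 0.208 m/s.

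The same amount appears as a spurious 6-to-18-month fall and is subtracted from the entry U+ versus U- difference.

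The last three columns give the chance that a two-sided paired t-test at 0.05 is significant in U+ when there is no true change after month 6. They assume the SD of change is 0.24 and treat the bias as a shift in the mean. Group sizes of 25, 50 and 75 are half of 50, 100 and 150, from the planned 50-150 subjects with about half U+.

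| f | g | Bias, m/s | % of 2.08 | n = 25 | n = 50 | n = 75 |
|---|---|---|---|---|---|---|
| 0.10 | 0.5 | 0.010 | 0.5 | 5.5% | 6.0% | 6.6% |
| 0.10 | 1.0 | 0.021 | 1.0 | 7.0% | 9.2% | 11.5% |
| 0.25 | 0.5 | 0.026 | 1.25 | 8.2% | 11.7% | 15.3% |
| 0.25 | 1.0 | 0.052 | 2.5 | 18.0% | 32.4% | 45.7% |
| 0.50 | 1.0 | 0.104 | 5.0 | 54.8% | 85.2% | 95.9% |

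The last row is an extreme corner: it fits poorly with visits that often coincide. If f or g is near zero, the bias is near zero and the test keeps roughly its nominal 5%.

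**The case against.** The strongest reply is that drug status at the entry scan is inferred from silence. That is right, and it rules out several stronger readings that a reader might be tempted to make.

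- **That the gap goes unrecorded.** The documents show only that they contain no data item or rule for it. The parent FUEL and FUEL-OLE records may hold dose dates, and section 11.1 labels scans and samples with the FUEL Extension identification number, so linkage is feasible.
- **That separate-visit subjects go days or weeks without drug.** No gap length appears anywhere.
- **That same-visit subjects are also off drug at the scan, while their OLE-D1 blood, echocardiogram, EndoPAT and exercise tests are on drug.** For them any interruption may be only about overnight. Whether an effect fades in that time depends on information the documents do not give.
- **That the two scans are wholly unaligned.** Section 11.1 prefers first-of-day imaging at both visits and offers hotel costs to make it possible at 12 months. End-of-day imaging remains allowed, so alignment is likely but not assured.
- **That the main analysis should drop U+ subjects with separate visits.** Restricting only U+ could damage the entry contrast, because visit coincidence may vary with site or calendar time.

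The scope is also limited. The primary aim is descriptive, the U- before-and-after analysis is not affected, and section 9.1 defers data conventions to a SAP still to be written.

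What stands is that sections 5.0 and 9.4.3 give every U+ entry scan an on-treatment label that the section 11.1 schedule does not guarantee, and that the plan as written offers no way to tell a small effect of this from a large one.

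**Conclusion.** The point holds for U+ subjects whose last FUEL day and OLE-D1 were separate visits. Their 6-to-18-month change may compare a scan after a treatment interruption with an on-treatment scan. The direction of the bias follows from the plan's own hypothesis: a spurious further fall in U+, and a smaller U+ versus U- difference at entry.

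The size cannot be fixed from the documents. Over f = 0.10 to 0.50 and g = 0.5 to 1.0 it runs from 0.010 to 0.104 m/s (0.5% to 5.0% of 2.08). It rests on four assumptions: a true 10% effect, at least partial reversal without drug, a non-trivial share of separate visits, and an on-treatment final scan. The last is implied by a year of treatment but not stated.

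The documents do not support a conclusion that the entry scans as a whole are off drug. The point warrants a change because the remedy is cheap and the dose-to-scan interval is hard to recover reliably afterwards.

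**What to change.** 1. Reconcile sections 5.0, 9.4.3 and 11.1, so that the 6-month and 18-month labels match when the scans are actually taken.
2. Record at both visits the date and time of the last study-drug dose and of the scan. Merge FUEL last-dose dates from the parent trial after unblinding. Report the dose-to-scan interval by group and visit.
3. Keep the 12-month scan in the same first-of-day morning slot as the entry scan where the FUEL-OLE visit allows, without altering dosing.
4. Keep all U+ subjects in the main analysis.
5. Pre-specify in the SAP a sensitivity analysis of the U+ 6-to-18-month change limited to subjects whose OLE-D1 was the FUEL final visit. For the U+ versus U- entry contrast, apply the same restriction to both groups.

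Cost: two CRF fields, one data merge, and a smaller and less precise sensitivity set.
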